9.4.3 Analysis of The Secondary Endpoint(S)

Key secondary endpoint (hierarchical composite of death and time-averaged KCCQ)

The key secondary endpoint is a hierarchical composite of **(1) all-cause death** and **(2) time-averaged KCCQ overall summary score** within a shared follow-up period by a pair of patients, evaluated using the win ratio framework. Pairwise comparisons will prioritize death; among pairs tied on death status, the KCCQ component will be evaluated using the **time-averaged KCCQ overall summary score** over follow-up. Time-averaged KCCQ will be calculated using all available post-baseline KCCQ assessments and weighted by the time between assessments (i.e., a time-weighted average). The win ratio, 95% confidence interval, and p-value will be reported.

Additional secondary endpoints

Secondary endpoints include patient-reported outcomes, functional outcomes, clinical events, and imaging outcomes as prespecified in Table 1. These will be analyzed using methods appropriate to the endpoint type:

1. **Time-to-event endpoints** (e.g., all-cause death, cardiovascular death, any stroke, disabling stroke, rehospitalization, composite clinical endpoints, aortic dissection, need for surgery of the aorta, BVF/SVD): cumulative incidence functions will be plotted considering non-cardiac death as competing risk for cardiac death; all-cause death as competing risk for any stroke, disabling stroke, rehospitalization, recovery based on QOR-15, aortic dissection, need for surgery of the aorta, BVF/SVD, and need of surgery of aorta as competing risk for aortic dissection. Time-to-event models accounting for competing risk and stratification factors will be used. Results will be summarized as hazard ratios or cumulative incidences with 95% confidence intervals.
2. **Binary endpoints** (e.g., presence of moderate/severe PVL at prespecified timepoints, recovery based on QOR-15, ascending aorta dimension >50 mm, NYHA class): Logistic regression models for repeated measures will be fitted with time, as a categorical covariate, treatment and the interaction between treatment and time as fixed effects. Additionally, models will adjusted by the stratification factors. Results will be summarized as odds ratios between study arms with 95% confidence intervals.
3. **Continuous endpoints** (e.g., KCCQ at each follow-up timepoint, SF-12 component scores, 6-minute walk distance, PHQ-9, time-averaged KCCQ): For longitudinal continuous outcomes, linear mixed models will be fitted with baseline outcome value, time as a categorical covariate, study arm and the interaction between treatment and time as fixed effects. Additionally, models will adjusted by the stratification factors. A subject-specific random effect will be included to describe the correlation between measures over time. Estimates will be presented as mean differences between study arms with 95% confidence intervals at prespecified timepoints. For change in ascending aorta dimension, time will be considered as a continuous covariate to estimate mean difference in annualized change

between study arms with 95% confidence interval. For time-averaged KCCQ, linear regression will be fitted with treatment as main covariate adjusted by the stratification factors. Mean difference between study arms will be presented with 95% confidence interval.

4. **Rate/count endpoints** (e.g., cardiovascular rehospitalization days): Negative Binomial model will be fitted with study arm as main covariate adjusted by the stratification factors and offset by days alive and out of hospital. Incidence rate ratio between study arms will be estimated with 95% confidence interval.

9.4.4 **Multiplicity and Control of Type I Error**

Multiplicity and Control of Type I Error. To control the overall family-wise type I error rate at two-sided $\alpha = 0.05$, hypothesis testing will follow a prespecified gatekeeping (hierarchical) procedure. First, the primary endpoint will be tested at two-sided $\alpha = 0.05$. Only if the primary endpoint is statistically significant will the key secondary endpoint be tested at two-sided $\alpha = 0.05$. Only if both the primary and key secondary endpoints are statistically significant will confirmatory testing proceed to a prespecified family of additional secondary endpoints.

For this family of additional secondary endpoints, multiplicity will be controlled using the Holm step-down procedure at two-sided $\alpha = 0.05$. The set of endpoints included in the Holm family (and any prespecified rules for missing data and estimands) will be fully specified in the Statistical Analysis Plan.

9.4.5 **Safety Analyses**

AEs will be summarized as the number and percentage of participants experiencing at least one event, overall and by study arm. In addition, exposure-adjusted incidence rates (events per 100 patient-years) will be presented when appropriate to account for differences in exposure duration. For each AE the following will be recorded: seriousness, start date, stop date, severity, relationship, expectedness, and outcome. Adverse events leading to premature discontinuation from the study intervention and serious treatment-emergent AEs will be presented in a listing.

9.4.6 **Sub-Group Analyses**

We recognize that any overall treatment effect may not apply equally to all patients, so the use of subgroup analyses to explore such potential heterogeneity is of enormous value. Thus, we will pre-define key patient characteristics that will form the basis for subgroup analyses and their associated tests of heterogeneity. We have the relevant statistical expertise on this topic (e.g. Pocock et al, *Statistical Controversies in Reporting of Clinical Trials*, JACC 2015;66:2648-62(7)). While enquiries into heterogeneity of effects are useful, it is widely known that they have reduced statistical power. For instance, for the primary outcome we have 85% power under the assumption that the relative risk is 0.75. If such an effect truly splits into relative risks of 0.5 and 1.0 respectively in a subgroup analysis (an all-or-nothing interaction) this would be detectable with power slightly less than 60%. We will therefore also perform subgroup analyses of time-averaged KCCQ assuming a standard deviation of 14.5 for which we have adequate power to detect **heterogeneity of treatment effect**.

Sex: We will have 82% power to detect heterogeneity of the treatment effect between men and women (using a test of interaction with 5% significance) if the difference in the effect of time-averaged KCCQ between men and women is 5 units. This power is calculated for the mandated minimum 35% of women, and will be greater if the proportion of women actually recruited is higher.

Age: We will perform subgroup analyses according to age (<65 vs. ≥65 years). If the difference in the effect of TAVR vs. SAVR on time-averaged KCCQ between younger and older patients is 5 units, we will have 85% power to detect heterogeneity of treatment effect at a 5% significance level (alpha), assuming an approximately 50/50 split between age groups.

TAVR risk subgroup analysis: We will perform subgroup analyses according to TAVR risk strata (low vs. intermediate/high). If 25% of patients are considered intermediate/high TAVR risk and the difference in the effect of TAVR vs. SAVR between intermediate/high and low risk patients is 6 units, we will have 87% statistical

power.

SAVR risk subgroup analysis: We will perform subgroup analyses according to SAVR risk strata (low vs. intermediate/high). If 33% of patients are considered intermediate/high SAVR risk and the difference in the effect of TAVR vs. SAVR between intermediate/high and low risk patients is 6 units, we will have 92% statistical power.

The proposed plan was jointly devised with the input of [name]'s team from the London School of Hygiene & Tropical Medicine, who were responsible for the statistical planning and analysis of the PARTNER trials(8-10).

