Key Secondary	Hierarchical composite of (1) death (2) time averaged KCCQ score.	Win ratio	Survival status assessed at latest available annual follow-up. KCCQ will be assessed as a time-average over patient follow-up	>95%
Secondary	Time averaged Kansas City Cardiomyopathy Questionnaire (KCCQ) status (continuous)	KCCQ questionnaire	Time average over all patient follow-up	>95%
Secondary	Kansas City Cardiomyopathy Questionnaire (KCCQ) status (continuous)	KCCQ questionnaire	From baseline to 1, 12, 24, 36, 48, 60, 72, 84, 96, 108, 120 months	Not powered
Secondary	CV rehospitalization days (count)	CRF: clinical events assessed by direct follow-up	Event driven	Not powered
Secondary	Short Form-12 (SF-12) Health Survey (continuous)	SF-12 questionnaire	From baseline to 1, 12, 24, 36, 48, 60, 72, 84, 96, 108, 120 months	Not powered
Secondary	New York Heart Association (NYHA) status (categorical)	NYHA clinical scale	From baseline to discharge, 1, 12, 24, 36, 48, 60, 72, 84, 96, 108, 120 months	Not powered
Secondary	6 min walk test (continuous)	6 min walk test distance	From baseline to 1, 12	Not powered
Secondary	Depression score (continuous)	PHQ-9 score	From baseline to 1, 12, 24, 36, 48, 60, 72, 84, 96, 108, 120 months	Not powered
Secondary	Time-to-recovery to baseline (categorical)	QOR-15 scale	From baseline to discharge, 1, 12 months	Not powered
Secondary	Death (time-to-event)	CRF: clinical events assessed by direct follow-up	Event driven	Not powered
Secondary	Cardiovascular death (time-to-event)	CRF: clinical events assessed by direct follow-up	Event driven	Not powered
Secondary	All stroke (time-to-first event) Ischemic, hemorrhagic, not otherwise specified	CRF: clinical events assessed by direct follow-up	Event driven	Not powered
Secondary	Disabling stroke (time-to-first event,)	CRF: clinical events assessed by direct follow-up	Event driven	Not powered
Secondary	Rehospitalization (valve-, procedure-, or HF-related); (time-to-first event)	CRF: clinical events assessed by direct follow-up	Event driven	Not powered
Secondary	Death/stroke/rehospitalization; (time-to-first event)	CRF: clinical events assessed by direct follow-up	Event driven	Not powered
Secondary	Aortic dissection (time-to-first event)	CRF: clinical events assessed by direct follow-up	Event driven	Not powered
Secondary	Need for surgery of the aorta (time-to-event)	CRF: clinical events assessed by direct follow-up	Event driven	Not powered

[figure not shown]

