6.2 MEASURES TO MINIMIZE BIAS: RANDOMIZATION

Patients will be randomized 1:1 to TAVR or SAVR using a centralized, secure web-based randomization system managed by the Data Coordinating Center, employing permuted blocks with varying block sizes and stratified by: (1) sex and (2) low or intermediate/high SAVR (clinical) risk and (3) planned TAVR type (in the event of randomization to TAVR). This is an open-label study; patients, treating clinicians, and site staff will not be blinded to treatment assignment. Randomization will be adaptive to maintain balance in study arm allocation within each site.

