8 STUDY ASSESSMENTS AND PROCEDURES

8.1 SCREENING/BASELINE

The following screening and baseline assessments should be conducted within 90 days of index procedure, unless otherwise noted. All assessments marked with an asterisk (*) are required prior to the patient selection committee.

- Signed Informed Consent*
- Demographics and Medical History*
- Physical Exam and vital signs*
- STS risk score and EuroSCORE II*
- SYNTAX score only in the presence of coronary artery disease requiring intervention*
- Concomitant Cardiovascular Medications*
- NIH Stroke Scale (NIHSS) and Modified Rankin Scale (mRS)
- Laboratory Test (Complete Blood Count, Comprehensive Metabolic Panel, and NT-proBNP). Sites who do not have the capability to collect an NT-proBNP lab, a BNP lab will be accepted instead *
- Pregnancy test (only for women of childbearing potential)
- Pulmonary Function Test (PFT) only for patients with a history of severe lung disease
- 12-lead ECG*
- Transthoracic Echocardiogram (TTE)*
- NYHA classification and CCS angina*
- 6 min walk test
- Frailty index (ADLs, 5 Meter Walk Test, and Grip Strength)*
- Kansas City Cardiomyopathy Questionnaire (KCCQ)
- SF-12 Questionnaire
- QOR-15 scale (Quality of recovery)
- PHQ-9 scale (Depression score)
- 3D Cardiac contrast CT within 1 year of case review committee date. If a TEE or a cardiac MRI are available per standard of care within 6 months of the patient selection committee date, the images will be collected for the study. *
- Iliofemoral CT Angiography within 1 year of case review committee date*
- Invasive or CT coronary Angiography within 1 year of case review committee date*
- Patient Selection Committee will be scheduled after completion of all of the above assessments marked with an asterisk (*)

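### The NYHA logistic model leaves out the collected baseline NYHA class: the analysis stays valid, but some power is given up for no stated reason

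*Protocol*

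**What the plan says.** Protocol section 9.4.3, item 2 (binary endpoints), covers moderate or severe paravalvular leak and "recovery based on QOR-15, ascending aorta dimension >50 mm, NYHA class". For these endpoints "Logistic regression models for repeated measures will be fitted with time, as a categorical covariate, treatment and the interaction between treatment and time". The item then says: "Additionally, models will adjusted by the stratification factors. Results will be summarized as odds ratios between study arms". No baseline value is listed, and the item does not defer its covariates to the SAP. Elsewhere the protocol does defer openly: section 9.4.2 leaves the method of adjusting the win ratio to the SAP, and section 9.4.4 leaves the members of the Holm family to it.

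Item 3 of the same section (continuous endpoints) says that "linear mixed models will be fitted with baseline outcome value, time as a categorical covariate, study arm and the interaction between treatment and time".

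Under section 6.2 the stratification factors are sex, SAVR risk (low against intermediate or high) and planned TAVR type. Baseline NYHA class is not one of them. It is recorded at screening: section 8.1 lists "NYHA classification and CCS angina" with the asterisk that makes it mandatory before committee review, and the schedule in section 1.3 agrees. Table 1 gives NYHA as a categorical secondary outcome measured from baseline onward, not powered.

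**The concern.** Two adjacent items of one section treat the baseline differently, and no reason is given. For the continuous outcomes the baseline value is the first covariate named. For NYHA, whose baseline is just as available, it is missing, and no stratification factor stands in for it directly.

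A baseline measure of the same scale is usually among the better predictors of the follow-up value. Leaving it out of a logistic model pulls the odds ratio towards 1 and lowers the power of the treatment test. NYHA is one of three functional outcomes that section 3 sets against the objective of comparing function. Power that costs no patients and no visits is worth having there, and the covariate is best fixed before outcome data exist, the more so in an open-label trial.

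**Working it through.** **1. The plan's own figure.** The protocol gives no power for NYHA. Its only checkable sizing figure is for the primary endpoint: 85.3% with 1,020 patients (section 9.4.1). A simulation of 10,000 trials, 510 per arm, with the Table 2 distribution and ties within a clinical tier broken by event time, gave 84.7%. Dropout: 1,020 / (1 − 0.125) = 1,166, against 1,200 planned. Both agree with the plan, but neither bears on NYHA.

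**2. Evaluable patients.** 600 × (1 − 0.125) = 525 per arm, from the protocol's sample size and loss rate.

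**3. Simulation A: baseline effect as an odds ratio.** Let z be treatment (0 or 1) and x the worse NYHA class at baseline (0 or 1):

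logit P(Y = 1) = a + b·x + θ·z

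Assumed, not in the protocol: one visit, P(x = 1) = 0.35, control rate 30% (which fixes a), treatment OR exp(θ) = 1.4, baseline OR exp(b) from 1.5 to 10. Each setting used 1,500 trials. Power is the share with |Wald z| > 1.96, with x left out and with x included.

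| Baseline OR | Power without | Power with | Change (points) | Variance ratio, marginal log-OR |
|---|---|---|---|---|
| 1.5 | 71.1% | 71.0% | −0.1 | 1.00 |
| 2 | 69.7% | 70.1% | +0.4 | 0.97 |
| 3 | 66.4% | 69.9% | +3.5 | 0.94 |
| 5 | 59.5% | 65.3% | +5.8 | 0.88 |
| 10 | 47.6% | 59.1% | +11.5 | 0.74 |

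The last column is the variance of the baseline-standardised log-OR divided by that of the unadjusted one.

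**4. Where the gain comes from.** At baseline OR 3 the mean unadjusted estimate is 0.312 with SE 0.1315, so z = 2.37. The adjusted estimate is 0.334 with SE 0.1362, so z = 2.45. The SE rises, but the estimate moves further from zero. At baseline OR 10 the pairs are 0.249 / 0.1320 = 1.89 and 0.332 / 0.1533 = 2.17. So the conditional odds ratio gains power, not a smaller standard error. Only the marginal, standardised estimate becomes more precise.

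**5. Validity.** With treatment OR 1.0 and baseline OR 3, rejection was 4.6% without the baseline and 4.5% with it.

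**6. Simulation B: a latent normal scale.** Assumed: one visit, 525 per arm, follow-up cut at 0.5 SD and a shift of 0.195 SD. The rates are then 1 − Φ(0.5) = 31% and 1 − Φ(0.695) = 24%. Baseline is cut into four classes, with 1,500 trials per setting.

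| Latent correlation | Power without | Power with | Change (points) |
|---|---|---|---|
| 0.3 | 68.2% | 69.5% | +1.3 |
| 0.5 | 66.9% | 72.4% | +5.5 |
| 0.7 | 67.7% | 80.1% | +12.4 |

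A repeat with 4,000 trials and different baseline cuts gave +2.0, +5.9 and +12.1 points (Monte Carlo SE of each gain at most 0.7). Simulation A holds the conditional effect fixed and B the marginal effect, so unadjusted power falls with the association in A and stays level in B. The gains agree in direction and size.

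**The case against.** The strongest reply is that nothing here is wrong. Randomisation makes the comparison without the baseline valid, and its error rate already allows for chance imbalance. Nor does the protocol set a rule and then break it: the regression for time-averaged KCCQ in item 3 also uses only treatment and the stratification factors. The valve is replaced between the two NYHA measurements, so the association may be weak and the gain close to nil. NYHA is marked as not powered. All of this stands, and it limits the point to an optional gain in efficiency.

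It does not remove the point. Item 2 fixes the model's terms, the covariate is already collected, and where the association is weak the simulated cost of adding it was negligible.

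A reader might infer more than the documents support:

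- **Bias or a false-positive problem.** Step 5 shows neither.
- **The same loss for aorta above 50 mm.** Section 5.2 excludes patients with an ascending aorta of 45 mm or more, so baseline status on that outcome is the same for every eligible patient and adding it changes nothing. Continuous baseline diameter is a different covariate. No gain has been calculated for it, and the endpoint is exploratory.
- **A contradiction because Table 1 calls NYHA categorical.** Table 1 gives the same label to aorta above 50 mm, which is plainly binary. A proportional-odds model is a matter of preference with its own assumption, not a correction.
- **A threat to confirmatory testing.** Whether NYHA enters the Holm family is left to the SAP.

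**Conclusion.** The point holds as a low-priority improvement to the NYHA model. As written, the analysis is valid and gives up power: about 0 to 6 points for a weak to moderate baseline-outcome association (OR 1.5 to 5, or latent correlation 0.3 to 0.5) and about 11 to 12 points for a strong one (OR 10, or correlation 0.7). Only the number of evaluable patients comes from the protocol. The rates, the treatment effect, the single visit and the strength of association are all assumed, so the range shows what could be gained and does not forecast it. Paravalvular leak and QOR-15 recovery are not part of the point: a leak around the new prosthesis has no pre-implant value, and QOR-15 recovery already has the baseline in its definition.

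**What to change.** In section 9.4.3, item 2, name baseline NYHA class as a covariate in the NYHA model, alongside the stratification factors. State that the odds ratio is then conditional on baseline, and report a standardised (marginal) risk difference between arms with its 95% confidence interval. If some baseline classes are nearly empty, state in advance how they will be combined.

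Optionally, add continuous core-laboratory ascending aorta diameter at baseline to the exploratory model for aorta above 50 mm, with no claim of a known gain.

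The cost is a sentence or two in the protocol and one extra summary in the analysis. No new data, visits or patients are needed. The one drawback is that the conditional odds ratio no longer means the same as an unadjusted one, which is why the risk difference should stand beside it. The change should be made before outcome data are examined.

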Secondary	Bioprosthetic valve failure (BVF); (time-to-first event)	Echo corelab determined	Event driven	Not powered
Secondary	Paravalvular leak severity (categorical)	Echo corelab determined	From baseline to discharge, 1, 12, 24, 36, 48, 60, 72, 84, 96, 108, 120 months	Not powered
Safety	Valve-related mortality (time-to-event)	CRF: clinical events assessed by direct follow-up	Event driven	Not powered
Safety	Myocardial infarction	CRF: clinical events assessed by direct follow-up	Event driven	Not powered
Safety	Coronary obstruction	CRF: clinical events assessed by direct follow-up	Event driven	Not powered
Safety	Major bleeding (VARC-3)	CRF: clinical events assessed by direct follow-up	Event driven	Not powered
Safety	Major vascular complication (VARC-3);	CRF: clinical events assessed by direct follow-up	Event driven	Not powered
Safety	Cardiac structural complication (major)	CRF: clinical events assessed by direct follow-up	Event driven	Not powered
Safety	Need for open heart surgery	CRF: clinical events assessed by direct follow-up	Event driven	Not powered
Safety	Atrial fibrillation/ atrial flutter	CRF: clinical events assessed by direct follow-up	Event driven	Not powered
Safety	Need for permanent pacemaker	CRF: clinical events assessed by direct follow-up	Event driven	Not powered
Safety	Device malpositioning (including embolization and migration)	CRF: clinical events assessed by direct follow-up	Event driven	Not powered
Safety	Acute Kidney Injury stage 3-4	CRF: clinical events assessed by direct follow-up	Event driven	Not powered
Safety	Endocarditis (valve-related)	CRF: clinical events assessed by direct follow-up	Event driven	Not powered
Safety	Clinically significant valve thrombosis (time-to-first event)	CRF: clinical events assessed by direct follow-up	Event driven	Not powered
Exploratory	Prosthesis-patient mismatch severity (categorical)	Echo corelab determined	From baseline to discharge, 1, 12, 24, 36, 48, 60, 72, 84, 96, 108, 120 months	Not powered
Exploratory	Subclinical valve thrombosis (time-to-first event)	CT corelab determined	Event driven	Not powered
Exploratory	Ascending aorta dimension > 50 mm (categorical)	CT corelab determined	From baseline to standard of care interval CTA	Not powered
Exploratory	Change in ascending aorta dimension from baseline to follow up as cm/y (continuous)	CT corelab determined	From baseline to standard of care interval CTA	Not powered

[figure not shown]

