4. If the site does not have the capability to collect an NT-proBNP lab, a BNP lab can be collected instead.
5. Serum pregnancy test (only for women of childbearing potential).
6. Echocardiography can be done at any time post procedure before discharge
7. A 12-Lead ECG at 2-10 year follow-up will only be collected if done per standard of care.
8. Only for patients with history of severe lung disease.
9. A 3D cardiac imaging or Coronary Angiogram done within 1 year of the patient selection committee date can be used for screening. If a TEE or a cardiac MRI are available per standard of care within 6 month of the patient selection committee date, the images will be collected for the study.
10. 3D Cardiac Contrast CT will be performed following SOC as per ACC/AHA guidelines.
11. Selected medications.
12. It will be conducted at time of pre-procedure evaluation.

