- **Subclinical valve thrombosis (time-to-first event):** Imaging evidence of leaflet thrombosis (e.g., hypoattenuated leaflet thickening and/or reduced leaflet motion) with absent or mild hemodynamic changes and no symptoms or clinical sequelae.
- **Ascending aorta dimension >50 mm:** maximum ascending aorta diameter measured by CT Core Lab; endpoint met if >50 mm at any follow-up CT.
- **Change in ascending aorta dimension (cm/year):** annualized change in maximum ascending aorta diameter from baseline to follow-up CT by CT Core Lab.

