9.4 STATISTICAL ANALYSES

9.4.1 General Approach

Under the stated assumptions, we used 10,000 simulated trials to determine that 1020 patients with complete 3-year data achieves 85.3% power for a two-sided Finkelstein-Schoenfeld at a 5% significance level. Simulations randomly generated time-to-event data for each clinical event using an exponential distribution, with the rates for each component tailored so that the distribution of the most severe outcome within each patient followed the distribution given in Table 2. KCCQ outcomes were randomly generated from a binomial distribution. To allow for a small number of crossovers, loss-to-follow up (estimated at around an eighth or 12.5% of patients, in line with PARTNER trials), we propose to recruit a total of **1,200 randomized patients, 600 in each arm**. This sample size yields >95% power for the analysis of the key secondary outcome (a hierarchical composite of death and time-averaged KCCQ score) if SAVR improves the average KCCQ score by 3 points under the assumption that the standard deviation of an individual KCCQ measurement is 20. **Our key secondary outcome** is similar to the primary endpoint of the PCORI-funded RECHARGE study, which will study a hierarchical composite of death and SF-12 quality of life assessment, using the win ratio(5). Such a magnitude of improvement in KCCQ is regarded as clinically meaningful and, in context, is similar to that seen in novel heart failure drugs that have impacted survival and quality of life(6).

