9.4.8 Handling of missing data

The extent and pattern of missing data will be summarized by study arm and visit, including reasons for missingness when available.

For the Winratio analysis, participants without KCCQ at least 1-year post-randomization will have their KCCQ comparison considered as non-evaluable/tier, unless a higher-level component has already determined the winner.

For time-to-event endpoints, participants without an event will be right-censored at the last known contact date.

For longitudinal patient-reported and functional outcomes, models fitted by full maximum likelihood will be used, which provide valid inference under a missing-at-random (MAR) assumption conditional on included covariates and observed outcomes. As sensitivity analyses, departures from the MAR assumption will be assessed using delta-adjusted pattern-mixture models. Following multiple imputation under MAR, imputed outcome values occurring after permanent dropout will be systematically shifted by clinically meaningful offsets (δ) to reflect plausible worse (or better) unobserved outcomes. A range of δ values will be examined to evaluate robustness of conclusions.

For time-averaged KCCQ, missing KCCQ measurements will be imputed based on the the mean estimates from a linear mixed model with time as categorical covariate, study arm and the interaction between study arm and time as fixed effects and subject-specific random effects.

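### Change in ascending aorta dimension: continuous time with a single subject-specific random effect gives a too-narrow interval for the arm difference in growth if growth rates vary and patients have three or more, or irregularly spaced, follow-up CTs (minor)

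*Protocol*

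**What the plan says.** Protocol 9.4.3 item 3 sets out one model for continuous outcomes that are measured repeatedly: "linear mixed models will be fitted with baseline outcome value, time as a categorical covariate, study arm and the interaction between treatment and time". These terms form the fixed part, which is further adjusted for the stratification factors. Within-patient correlation is handled in one sentence: "A subject-specific random effect will be included to describe the correlation between measures over time".

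For the aorta, one element is changed: "For change in ascending aorta dimension, time will be considered as a continuous covariate to estimate mean difference in annualized change", to be reported with a 95% confidence interval. The target is therefore the arm-by-time slope. No random slope, other covariance structure or robust variance is stated for it.

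Section 3 defines the endpoint for each patient: "annualized change in maximum ascending aorta diameter from baseline to follow-up CT by CT Core Lab". Table 1 (section 1.1) lists it as exploratory and not powered, with timing "From baseline to standard of care interval CTA". The schedule in 1.3 marks cardiac CT in the 1-year, annual and event-driven columns, each with the footnote "3D Cardiac Contrast CT will be performed following SOC as per ACC/AHA guidelines". The number and spacing of CTs can therefore differ between patients.

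**The concern.** With categorical time and visit-by-visit contrasts, a single random intercept is usually tolerable. The difficulty comes from moving to continuous time, with a slope as the target, while leaving the random part unchanged. A random intercept lets patients start at different diameters, but within an arm they all grow at the same rate. Real differences in growth then fall into the residual, which the model treats as independent noise that averages out over scans. It does not average out: a patient who grows fast does so on every scan.

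The estimated difference itself is not in question; its standard error is. At stake is the coverage of the interval for aortic growth after TAVR versus SAVR, a question of particular interest in bicuspid disease.

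**Working it through.** The protocol gives no standard error, power or number of patients for this endpoint, so there is no stated figure to reproduce. The check asks how far the model's standard error falls short of the true one.

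**Inputs**
- From the protocol: one subject-specific random effect, continuous time and an arm-by-time target (9.4.3); "1,200 randomized patients, 600 in each arm" (9.4.1). The number with follow-up CT is not given, but it cancels from the closed form.
- Assumed, not in the documents: measurement SD s = 1 mm (0.10 cm); between-patient SD of growth rate τ = 0.2–0.5 mm/year (0.02–0.05 cm/year); the CT counts shown below.

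**Closed form, m follow-up CTs at common times.** Let Sxx be the within-patient sum of squares of time.
- A patient's fitted slope truly varies with variance s²/Sxx + τ².
- The random-intercept model estimates its residual variance as s² + τ²·Sxx/(m−1), so it reports s²/Sxx + τ²/(m−1).
- Multiplied by Sxx, the true value is s² + τ²·Sxx and the model's value is s² + τ²·Sxx/(m−1). They agree when m = 2, and the gap widens with m.

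Worked case, τ = 0.3, s = 1, years 1–6 (Sxx = 17.5):
- true: 1 + 0.09 × 17.5 = 2.575
- model: 1 + 0.09 × 17.5/5 = 1.315
- true SE / model SE = √(2.575/1.315) = 1.40
- a nominal 1.96 acts as 1.96/1.40 = 1.40, so about 16% of 95% intervals exclude the true difference.

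The same formula for yearly CTs, s = 1 mm:

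| CTs (m) | Sxx | Model SE / true SE, τ = 0.2 | Error rate | Model SE / true SE, τ = 0.5 | Error rate |
|---|---|---|---|---|---|
| 2 | 0.5 | 1.00 | 5.0% | 1.00 | 5.0% |
| 3 | 2 | 0.98 | 5.4% | 0.91 | 7.4% |
| 4 | 5 | 0.94 | 6.5% | 0.79 | 12.0% |
| 6 | 17.5 | 0.82 | 10.8% | 0.59 | 24.7% |

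**Simulation with no true arm difference** (REML, 150 patients per arm with CT, baseline as covariate, 300 trials per cell; simulation standard error about 1.3 points at 5%). Error rates for τ = 0.2 / 0.5:
- one CT: 6.3% / 4.3%
- two CTs, the second at an irregular time: 7.3% / 11.0%
- three CTs (years 1, 3, 5): 5.0% / 10.3%
- a mix of one to six CTs: 10.0% / 20.7%
- six CTs: 10.7% / 25.0%

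With τ = 0, where patients within an arm do share a rate, the error rate was 3.3–6.7% across all schedules. That isolates growth variation as the cause.

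**Sparser, irregular CTs over 6 years** (ML, 400 patients, s = 1 mm, τ = 0.1–0.5 mm/year, 600 runs per cell): mostly 1–2 CTs, 3–11%; mostly 1–3, 6–11%; a 1–4 mix, 5–9% for τ up to 0.3 and 15% at τ = 0.5.

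**With a random slope added** (60 trials per cell, so only the standard errors are informative), τ = 0.5 mm/year, model SE against empirical SE in cm/year:
- mix of one to six CTs: 0.0073 vs 0.0072 (intercept only: 0.0052 vs 0.0080)
- six CTs: 0.0063 vs 0.0072 (intercept only: 0.0038 vs 0.0068)

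**The case against.** The strongest reply is that the word intercept is not in the protocol. The sentence on the random effect is generic, written for KCCQ, SF-12, walk distance and PHQ-9 as well. Section 9.4.8 uses the plural for a similar KCCQ model ("interaction between study arm and time as fixed effects and subject-specific random effects"), so the singular is weak evidence of a deliberate choice. Random-effects structure is often settled in the SAP, and a random slope there would not clearly contradict 9.4.3. This stands in part: the SAP is a proper place for the fix. But an intercept is the natural reading of one subject-specific random effect, and an SAP that followed the sentence as written would carry the problem over.

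Three stronger readings are tempting, and the documents do not support them.
- A reader might infer error rates of 28–42%, or more, from ten annual CTs. Annual-CT figures are only an upper bound. Follow-up CT is per standard of care, the visit lists in 8.6 and 8.7 contain no CT, and exclusion criterion 7 removes aortas of 45 mm or more, so annual CT for everyone is not a safe base case.
- A reader might infer a false positive in a stated hypothesis test. Section 9.1 states a null only for the primary composite. For the aorta, 9.4.3 promises an estimate and an interval, and the gatekeeping in 9.4.4 does not extend to exploratory endpoints.
- A reader might infer that the model forces one growth rate on the whole trial, or that its interval is always too narrow. The arm-by-time term lets the arms differ, and with one CT, or two at common times, the interval is essentially right.

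**Conclusion.** The point holds as a conditional one. Under the natural reading of 9.4.3 item 3, the interval for the arm difference in annualized aortic change under-covers if growth rates vary between patients and patients have at least three follow-up CTs or irregularly spaced ones. Under the assumed SDs, the error rate at nominal 5% is roughly 5–15% for about 1–4 CTs per patient and about 10–25% with up to six. Growth SD, measurement SD and CT counts are all assumptions, and the result moves with each of them. Severity is minor: the consequence is confined to one exploratory, unpowered imaging endpoint, and no primary, key secondary or Holm-family conclusion depends on it.

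**What to change.** In 9.4.3 item 3, or in the SAP, state that the model for change in ascending aorta dimension includes a subject-specific random intercept and random slope for time. Name a patient-clustered robust variance as the fallback if that model does not converge, for example because most patients have only one follow-up CT.

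This takes one sentence and no new data. The cost is a wider interval. In the simulations with a mix of one to six CTs, the model SE rose from 0.0041 to 0.0047 cm/year at τ = 0.2 mm/year (0.0047/0.0041 = 1.15 times) and from 0.0052 to 0.0073 at τ = 0.5 (1.40 times). That is the width the data support.
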